## 2.4 Study Design

We intend to perform a prospective trial to determine the role of the combined  $^{18}\text{F}$  NaF/ $^{18}\text{F}$  FDG PET/MRI in the evaluation of skeletal metastases in patients with breast and prostate cancers. This study will be a comparative study that will investigate different types of bone scanning techniques. Patients will undergo preliminary evaluations to ensure eligibility, receive and sign informed consent, be enrolled in the trial, and then undergo the combined  $^{18}\text{F}$  NaF/ $^{18}\text{F}$  FDG PET/MRI. Patients will be followed clinically by 12-months post scan evaluation.

Patients who present to the Nuclear Medicine and Molecular Imaging Clinic for a  $^{99\text{m}}\text{Tc}$  MDP bone scan as part of their routine disease work-up/standard of care will be asked to participate in this study. If agreeable, written informed consent will be obtained by a member of the research team after explaining the risks, benefits, and procedures of the study. We will follow Stanford guidelines for screening patients for renal function prior to PETMRI if they are getting contrast. All scans will be performed within a 1-month timeframe. Blind interpretation of the combined  $^{18}\text{F}$  NaF/ $^{18}\text{F}$  FDG PET/MRI will be performed by Nuclear Medicine and Radiology readers. A direct comparison for each detected lesion will be performed among the imaging modalities.

We will attempt to recruit patients who are referred for a  $^{99\text{m}}\text{Tc}$  MDP bone scan for detection of skeletal metastases. In a typical year, approximately 3,500  $^{99\text{m}}\text{Tc}$  bone scans are performed in our Clinic, 90% (3,150) of them with referral for osseous metastases identification. We plan to recruit 40 patients per year for 2 consecutive years. Cancers with highest potential to metastasize to the skeleton (breast and prostate cancers) will be considered.

All age ranges of adult population (>18-year-old) will be recruited. Both men and women will be recruited. All ethnic background will be recruited. No healthy volunteers will be recruited. Pregnant women will be excluded because of the risk posed by unnecessary radiation to the fetus. Patients with metallic implants (prosthesis, ICD, pacemakers) will be excluded since these are contraindications for MRI.

The subjects will be paid \$150 to participate in this protocol. No costs will be charged to the subjects.

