#### **5.3 Details of processing/analysis**

The PET/MRI scans will be interpreted by 2 ABNM certified Nuclear Medicine physicians ([name], [name]) and 2 ABR certified Radiologists ([name], [name]) with significant clinical experience, blinded to the subjects' medical history and the results of other imaging modalities. The outcomes of the imaging methods will be analyzed and compared against each other. Consensus read will be obtained for each scan. Characterization of lesions as true positive, true negative, false positive or false negative will be done through a combination of clinical follow up, imaging follow-up and/or histopathology findings (when possible). For purposes of this study, the investigators will document an overall diagnosis of the findings for each scan on a 5 point scale to permit a receiver operating characteristic (ROC) analysis (1=benign, 2=likely benign, 3=uncertain, 4=likely malignant, 5=malignant). If the diagnosis is positive for metastases on any of the scans, the investigator will identify the number of lesions and locations of positivity, and record this information.

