**6. STUDY PROCEDURES & DETAIL**

**6.1 Criteria for Removal from Study**

The Protocol Director may withdraw subjects from the study for one or more of the following reasons: failure to follow the instructions of the Protocol Director and/or study staff; determination that continuing the participation could be harmful to the subject; the study is cancelled or other administrative reasons.

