## 10. STATISTICAL CONSIDERATIONS

### 10.1 Populations

Patients with  $\geq$  stage 3 breast cancer or  $\geq$  stage 2 prostate cancer (and/or PSA >10 micrograms/L), including patients with recurrent breast or prostate cancer will be enrolled. The analysis subset will consist of patients with an interpretable  $^{99m}\text{Tc}$  MDP

bone scan,  $^{18}\text{F}$  NaF/ $^{18}\text{F}$  FDG PET/MRI evaluations, and a known clinical bone lesion evaluation at 12 months.

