## 10.2 Key Variables

Diagnostic bone metastases status using  $^{99\text{m}}\text{Tc}$  MDP bone scan,  $^{18}\text{F}$  NaF/ $^{18}\text{F}$  FDG PET/MRI, bone metastases status at 12 months (all binary)

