## 10.3 Endpoints

**Primary:** concordance between  $^{99\text{m}}\text{Tc}$  MDP bone scan and  $^{18}\text{F}$  NaF/ $^{18}\text{F}$  FDG PET/MRI, as the proportion of patients where the modalities agree.

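### The month-12 requirement in section 10.1, read literally, drops patients whose bone metastasis was confirmed earlier, and it also removes them from the primary concordance analysis, which needs no reference standard

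*Combined protocol and SAP*

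**What the plan says.** - **Analysis set.** Section 10.1 names a single subset for all endpoints. Besides interpretable bone scan and PET/MRI results, it requires "and a known clinical bone lesion evaluation at 12 months".
- **Reference variable.** Section 10.2 lists "bone metastases status at 12 months (all binary". There is no category for earlier confirmation, death or unknown status.
- **Sources of truth.** Section 5.3 says that classifying lesions as true or false positive or negative "will be done through a combination of clinical follow up, imaging follow-up and/or histopathology findings (when possible". It gives no time point.
- **Follow-up.** Section 2.4: "Patients will be followed clinically by 12-months post scan evaluation". The study calendar in section 7 has one follow-up point, at 12 months.
- **Withdrawal.** Section 6.1: "The Protocol Director may withdraw subjects from the study for one or more of the following reasons". It does not say what becomes of a withdrawn patient's reference status.
- **Primary endpoint.** Section 10.3 defines concordance of the two modalities "as the proportion of patients where the modalities agree". The reference standard does not enter the calculation.
- **Secondary endpoints.** Sensitivity, specificity, PPV, NPV, and concordance in cases and in controls all need the reference.

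Section 10 contains no missing-data rule, no sensitivity analysis for unverified patients and no dropout allowance.

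**The concern.** Take a patient with a biopsy-proven bone metastasis at month 2 who dies at month 8. Section 5.3 would accept the biopsy as truth. Section 10.1 asks for an evaluation at month 12, which this patient cannot have. Nothing in the plan carries the earlier confirmation forward.

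Three things are at stake.

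1. **Verified cases are lost.** Section 10.5 puts the number of cases needed at 83 to 284, while the two PET/MRI cohorts together hold 80 + 50 = 130 patients, cases and controls combined. Section 10.4 also withholds any estimate with a denominator below 10 and reports by disease.
2. **Exclusion may be informative.** Entry is by stage 3 or higher breast cancer, stage 2 or higher prostate cancer (and/or raised PSA), or recurrence. A link between early death and bone disease is plausible, though the documents do not quantify it.
3. **The primary analysis is cut too.** Because there is only one subset, a patient with two readable scans and no month-12 evaluation also leaves the concordance and kappa calculation.

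**Working it through.** **Inputs.** From the Appendix: bone scan sensitivity 0.80, target gain Delta = 0.10, discordance K = 0.11 or 0.30. Cell probabilities among cases:

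| Cell | K = 0.11 | K = 0.30 |
|---|---|---|
| A, both positive | 0.795 | 0.700 |
| B, PET/MRI only | 0.105 | 0.200 |
| C, bone scan only | 0.005 | 0.100 |
| D, both negative | 0.095 | 0.000 |

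Alpha and power are not stated. I infer two-sided 0.05 and 80% because these reproduce the Appendix. Loss fractions and prevalence below are my assumptions.

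**Step 1: reproduce the plan's figure.** With P01 = (K - Delta)/2 and psi = (K + Delta)/(K - Delta):

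- K = 0.11: psi = 21, P01 = 0.005; n = (1.960 × √22 + 0.8416 × √20)² / 2 = 83.94, so 84.
- K = 0.30: psi = 2, P01 = 0.1; n = (1.960 × √3 + 0.8416 × √2.9)² / 0.1 = 233.09, so 233.

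Both match the Appendix. The upper figure of 284 in section 10.5 does not follow at these settings; that is a separate item to reconcile.

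**Step 2: effect of loss on the sensitivity difference.** If a fraction r of each cell is retained,

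difference = (rB·B - rC·C) / (rA·A + rB·B + rC·C + rD·D).

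Example, K = 0.11, losing 40% of both-positive cases and 10% of the rest: 0.9 × (0.105 - 0.005) / (0.6 × 0.795 + 0.9 × 0.205) = 0.090 / 0.6615 = 0.136.

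Example, K = 0.30, losing 30% of PET/MRI-only cases and 10% of the rest: (0.7 × 0.200 - 0.9 × 0.100) / (0.7 × 0.200 + 0.9 × 0.800) = 0.050 / 0.860 = 0.058.

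| Assumed loss among cases | K = 0.11 | K = 0.30 |
|---|---|---|
| 20% in every cell | 0.100 | 0.100 |
| 20% of both-positive, 10% of the rest | 0.110 | 0.108 |
| 30% of both-positive, 10% of the rest | 0.121 | 0.118 |
| 40% of both-positive, 10% of the rest | 0.136 | 0.130 |
| 10% of both-positive, 30% of the rest | 0.081 | 0.083 |
| 30% of PET/MRI-only, 10% of the rest | 0.078 | 0.058 |

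The table illustrates and does not bound the effect. Losing 30% of all bone-scan-positive cases and 10% of the rest, for instance, gives 0.123 and 0.149.

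**Step 3: effect on concordance.** Among cases, agreement is (A + D) over the total. At K = 0.11 it starts at 0.890. With 30% loss of both-positive cases and 10% of the rest it becomes 0.642 / 0.741 = 0.866; with 30% loss of PET/MRI-only cases and 10% of the rest it becomes 0.911.

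**Step 4: precision and prevalence.** Assume 130 patients and 50% prevalence, so 65 cases and 65 controls. Solving the Appendix formula for power, 65 cases give 69% (K = 0.11) and 31% (K = 0.30). After 20% case loss, 52 cases give 59% and 26%. With 20% loss in cases and 5% in controls, analysed prevalence is 52 / (52 + 61.75) = 45.7% instead of 50%, which shifts PPV and NPV.

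**Step 5: after the fix.** If every lost case had been confirmed before leaving, retaining them restores 0.80, 0.90 and a difference of 0.10.

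**The case against.** The strongest reply is that section 10.1 asks for a known evaluation and section 10.2 names a status, not an attended visit. A metastasis proven at month 2 can reasonably be called known at month 12. Section 5.3 speaks of lesions and is silent on timing, so its follow-up may be the same 12-month follow-up. This stands to the extent that the sections are ambiguous together and do not plainly contradict each other. It does not remove the problem: two analysts could build different analysis sets from the same data, and the literal reading excludes the patient.

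A reader might go further and infer that cases are lost selectively and that the PET/MRI advantage is therefore inflated. The documents do not support that.

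- They give no death, withdrawal or loss rates. Entry includes stage 2 prostate cancer, and the withdrawal grounds in section 6.1 include failure to follow instructions and administrative reasons, which have no evident link to bone disease.
- Higher loss in cases than in controls does not by itself bias sensitivity or the paired difference. Loss must also vary with scan result among cases.
- The direction is open. Losing both-positive cases raises the difference; losing PET/MRI-only cases lowers it; equal loss leaves it at 0.100. An example in which only both-positive cases go, such as 45/50 - 40/50 = 0.100 becoming 35/40 - 30/40 = 0.125, shows one extreme pattern. Under milder selection (20% against 10%) the shift is about one percentage point.

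A reader might also infer that the primary endpoint is untouched because concordance needs no reference standard. That is not so under section 10.1, since the same subset governs it.

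**Conclusion.** The point holds as a gap in the analysis-set rule. As written, sections 10.1 and 10.2 exclude patients who leave before month 12, with no exception for metastasis already confirmed by a source that section 5.3 accepts.

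Two consequences need no assumption about selectivity: any such patient is a verified case lost to the reference-based endpoints, and an unnecessary exclusion from the primary concordance analysis. Bias in the sensitivity difference is possible but not shown. Under the tabulated patterns, the planned 0.10 would be estimated at roughly 0.06 to 0.14. Under 20% case loss, power falls by about 10 percentage points at K = 0.11 and 5 at K = 0.30. These figures rest on assumed loss fractions, 50% prevalence, inferred alpha and power, and on taking the two groups in section 10.4 to be the PET/MRI cohorts of 80 and 50. The amendment should be made before the data are analysed.

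**What to change.** Amend sections 10.1, 10.2 and 10.4 as follows.

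1. For sensitivity, specificity, PPV, NPV, and concordance in cases and in controls, count a patient as reference-positive if bone metastasis was confirmed by any section 5.3 source (histopathology, imaging follow-up or clinical follow-up) at any time up to month 12, even if the patient later dies, withdraws or is lost.
2. Keep the 12-month evaluation as the requirement for reference-negative status, so that an early negative image alone does not make a control.
3. Treat patients who leave earlier without confirmation as unverified. Report their number by bone scan and PET/MRI result, and give sensitivity and specificity counting them first all as cases and then all as controls.
4. Compute primary concordance and kappa in all patients with both scans interpretable.

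**Cost.** Revised wording, one bounding table, and a record of the date and source of each confirmation; no new scan or visit.

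**Downside.** Early confirmation is likely to follow a positive scan. Keeping early-confirmed positives while early unverified patients are missing can therefore raise apparent prevalence, PPV and sensitivity. The bounds and the verification dates must be reported alongside the main estimates for that reason.

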## 10.2 Key Variables

Diagnostic bone metastases status using  $^{99\text{m}}\text{Tc}$  MDP bone scan,  $^{18}\text{F}$  NaF/ $^{18}\text{F}$  FDG PET/MRI, bone metastases status at 12 months (all binary)

## 10.3 Endpoints

**Primary:** concordance between  $^{99\text{m}}\text{Tc}$  MDP bone scan and  $^{18}\text{F}$  NaF/ $^{18}\text{F}$  FDG PET/MRI, as the proportion of patients where the modalities agree.

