## PROTOCOL SYNOPSIS

In the table below summarize the basic aspects of this research. This is to be used as a quick reference guide. Remove any section that is not relevant to the research.

TITLE	Combined $^{18}\text{F}$ NaF/ $^{18}\text{F}$ FDG PET/MRI for Detection of Skeletal Metastases
INDICATION	Breast cancer, lung cancer, prostate cancer
INVESTIGATIONAL PRODUCT OR PROCEDURE	$^{18}\text{F}$ NaF/ $^{18}\text{F}$ FDG PET/MRI
PRIMARY OBJECTIVE	Testing the hypothesis that the new simultaneous combined $^{18}\text{F}$ NaF/ $^{18}\text{F}$ FDG PET/MRI provide improved diagnostic accuracy over $^{99\text{m}}\text{Tc}$ MDP bone scanning
SECONDARY OBJECTIVE	
 
Evaluating the combined <math>^{18}\text{F}</math> NaF/<math>^{18}\text{F}</math> FDG PET/MRI as a reliable bone scanning modality
 
Evaluating the performance and reliability of the proposed WBMRI sequences
 

TREATMENT SUMMARY	No treatment
SAMPLE SIZE	170 participants: 10 from the pilot phase, 30 from PET/CT vs. WBMRI, 80 from first version of combined $^{18}\text{F}$ NaF/ $^{18}\text{F}$ FDG PET/MRI and 50 from second version of combined $^{18}\text{F}$ NaF/ $^{18}\text{F}$ FDG PET/MRI
STATISTICAL CONSIDERATIONS	
 
Per patient: concordance in cases, concordance in controls, sensitivity, specificity, positive predicted value, negative predictive value
 
Per lesion: distribution of lesions seen on each modality
 

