## 1. **OBJECTIVES**

### 1.1. **Primary Objective**

Testing the hypothesis that the combined  $^{18}\text{F NaF}/^{18}\text{F FDG PET/MRI}$ , either alone or in combination, provide improved diagnostic accuracy over  $^{99\text{m}}\text{Tc MDP}$  bone scanning

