### Secondary:

- Per patient: concordance in cases, concordance in controls, sensitivity, specificity, positive predicted value, negative predictive value
- Per lesion: distribution of lesions seen on each modality
- Proportion of diagnostic quality scans using the faster protocol compared to first cohort of 80 participants

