## 10.4 Plan of Analysis

The principal analysis will aggregate patients from the two groups and will be conducted on a per-patient basis. We will calculate the concordance between the modalities across outcomes (combining cases and controls) and evaluate the results by calculating the kappa coefficient. Secondary endpoints will be calculated, both as aggregates of the three diseases and separately by disease. Sensitivities and other summaries will only be calculated if they involve a denominator of at least 10.

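### The primary endpoint, pooled agreement and kappa between the two scans, cannot show the direction of a difference in accuracy, and section 10 specifies no paired comparison that could

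*Combined protocol and SAP*

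**What the plan says.** - **Objective.** The Protocol Synopsis poses the hypothesis that PET/MRI will "provide improved diagnostic accuracy over" bone scanning. Section 1.1 repeats it with "either alone or in combination, provide improved diagnostic accuracy over". This is a directional claim about accuracy.
- **Primary endpoint (10.3).** Concordance of the two scans, defined "as the proportion of patients where the modalities agree".
- **Principal analysis (10.4).** "The principal analysis will aggregate patients from the two groups", per patient. Then: "We will calculate the concordance between the modalities across outcomes (combining cases and controls) and evaluate the results by calculating the kappa coefficient".
- **Secondary endpoints (10.3).** Per patient: "concordance in cases, concordance in controls, sensitivity, specificity, positive predicted value, negative predictive value". Section 10.4 says that these will be calculated, subject to a minimum denominator of 10. It gives no difference between scans, no interval and no test.
- **Reference standard (10.1, 10.2).** A known 12-month bone evaluation is a condition for entering the analysis set, and 12-month status is listed as a binary key variable beside the two scan results.
- **Sizing (10.5, 10.7, Appendix).** The worked examples concern a paired 10-point gain in sensitivity among cases, from 0.80 to 0.90. Section 10.7 ties continued accrual to the sample size described there, but no single N is named.
- **Other comparisons.** Section 2.4 states: "A direct comparison for each detected lesion will be performed among the imaging modalities". Section 5.3 records a 5-point score for each scan so that an ROC analysis is possible. Section 10 does not carry the ROC analysis forward.

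**The concern.** The hypothesis asks which scan is closer to the truth. The primary statistic asks only how often the scans give the same answer. Two scans can disagree because the new one finds metastases that the old one misses, or because it misses metastases that the old one finds. Agreement and kappa count both alike.

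At stake is the headline result. If the plan is followed as written, any claim of improved accuracy must come from secondary estimates whose difference has no planned interval or test. Yet every analysed patient must already have the two scans and the 12-month status that a direct paired comparison needs.

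**Working it through.** **1. The plan's own figures.** The Appendix classifies cases as A (both scans positive), B (new only), C (old only) and D (neither), with K = B + C and Δ = B − C. Then P01 = (K − Δ)/2, ψ = (K + Δ)/(K − Δ), and

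n = [z_α√(ψ+1) + z_β√(ψ+1−(ψ−1)²P01)]² / [(ψ−1)²P01].

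Alpha and power are not stated. Two-sided 0.05 and 80% power (z = 1.960 and 0.842) are inferred because they reproduce both results:

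- K = 0.11: ψ = 21, P01 = 0.005; n = (1.960√22 + 0.842√20)²/2 = 83.9, matching 84.
- K = 0.30: ψ = 2, P01 = 0.1; n = (1.960√3 + 0.842√2.9)²/0.1 = 233.1, matching 233.

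This formula sizes a paired test of B against C among cases, which is not the quantity in 10.3.

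**2. Symmetry.** Agreement is po = A + D. Kappa is (po − pe)/(1 − pe), with pe = (A+B)(A+C) + (C+D)(B+D). Exchanging the scans swaps B and C, and both po and pe stay the same. In the Appendix's K = 0.11 table, po = 0.89, pe = 0.9×0.8 + 0.1×0.2 = 0.74 and kappa = 0.15/0.26 = 0.577, whichever scan has the sensitivity of 0.90. In the K = 0.30 table, po = 0.70 and kappa = −0.154 both ways. This step needs no assumption.

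**3. The pooled statistic as planned.** Assumed: 40% prevalence, and a control table (0.05, 0.05, 0.05, 0.85), that is, specificity 0.90 for both scans and 10% discordance. Case tables, with K held fixed:

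- Gain: the Appendix tables, (0.795, 0.105, 0.005, 0.095) and (0.70, 0.20, 0.10, 0.00).
- No gain (both sensitivities 0.80): (0.745, 0.055, 0.055, 0.145) and (0.65, 0.15, 0.15, 0.05).
- Loss: the gain tables with B and C swapped.

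For K = 0.11, po = 0.4×0.89 + 0.6×0.90 = 0.896 in all three situations. With a gain, the pooled positive rates are 0.42 and 0.38, so pe = 0.5192 and kappa = 0.3768/0.4808 = 0.7837. With no gain they are 0.38 and 0.38, so pe = 0.5288 and kappa = 0.3672/0.4712 = 0.7793.

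| K in cases | Agreement, all three | Kappa: gain | Kappa: no gain | Kappa: loss |
|---|---|---|---|---|
| 0.11 | 0.896 | 0.784 | 0.779 | 0.784 |
| 0.30 | 0.820 | 0.626 | 0.618 | 0.626 |

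The constant agreement within a row follows from holding K fixed; moving between rows does change it. At 20% and 50% prevalence the three kappas also stay within 0.011 of each other.

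**4. Unequal specificities.** With equal specificities, kappa for a gain and a loss must match exactly, so this was relaxed. The grid had 144 combinations: prevalence 20, 30, 40 and 50%; K = 0.11 and 0.30; specificity pairs 0.90/0.80, 0.95/0.85 and 0.95/0.75 in both orders; control discordance equal to the gap plus 0, 0.04 or 0.10. Reversing the sensitivity gain alone moved kappa by at most 0.005 (10-point gap) or 0.012 (20-point gap). The full spread over gain, no gain and loss reached 0.019 and 0.020.

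**5. What a paired analysis could deliver.** Assume that the two groups in 10.4 are the 80 and the 50 PET/MRI patients (130, no losses) and that prevalence is 20–50%. Then there are 130×0.20 = 26 to 130×0.50 = 65 cases. Exact McNemar power for a 10-point gain, two-sided 0.05:

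| Cases | K = 0.11 | K = 0.30 |
|---|---|---|
| 26 | 0.04 | 0.07 |
| 39 | 0.19 | 0.13 |
| 52 | 0.40 | 0.19 |
| 65 | 0.59 | 0.24 |

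**The case against.** **Agreement is not uninformative.** A reader might infer that the primary statistic can neither support nor refute the hypothesis. That goes too far. Pooled discordance must be at least prevalence × |Δ|, so a true 10-point sensitivity gain caps agreement at 0.98, 0.96 or 0.95 for prevalence 20%, 40% or 50%. Agreement above the cap excludes that gain, and perfect agreement excludes any improvement. This stands: concordance limits the size of a difference, but gives no direction and cannot establish improvement.

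**Accuracy is not ignored.** Sensitivity and concordance in cases are both secondary endpoints. If sensitivity is reported for both scans, their difference gives B − C and one minus the concordance gives B + C. Both discordant cells, and hence a paired difference and interval, can be recovered. The same holds for specificity and concordance in controls. So a reader should not infer that the information is lost. What is missing is a named contrast with its interval or test, in the primary position.

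**The superiority comparison is implied.** Sections 10.5 and 10.7 and the Appendix frame sizing and accrual around it. That shows what the authors had in mind. Section 10.5 treats concordance as an input to sample size, however, and neither 10.3 nor 10.4 turns the superiority comparison into an analysis.

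**The trial is small for a paired test.** True over the assumed range, but low power is a reason to show the uncertainty of the right quantity, not to make a different quantity primary.

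**Conclusion.** The concern holds. The primary endpoint and principal analysis do not address the primary objective, and section 10 contains no paired comparison of accuracy. The symmetry result is algebraic and rests on no assumed value.

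The numerical illustration is conditional. At the same discordance, and under the assumptions shown, agreement is identical and kappa differs by less than 0.01 at 40% prevalence between a 10-point gain, no gain and a 10-point loss. With specificities 10 to 20 points apart the spread in kappa is about 0.02 at most. It would be wrong to read this as saying that agreement never moves: it falls from 0.896 to 0.820 as K rises from 0.11 to 0.30.

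The case counts and powers are not ceilings either. The documents give no prevalence, and more cases would raise the power. At a 70% case share (91 cases) the normal approximation gives 0.83 (K = 0.11) or 0.41 (K = 0.30); it can run above the exact figure, for example 0.69 against 0.59 at 65 cases with K = 0.11.

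**What to change.** In 10.3 and 10.4:

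1. Make the primary analysis a paired comparison of accuracy against 12-month status. The choice that matches the Appendix is the paired difference in per-patient sensitivity (PET/MRI minus bone scan) among reference-positive patients, reported with the paired difference in specificity among reference-negative patients. Give each a 95% paired score interval, with exact McNemar as the supporting test. A paired ROC comparison of the 5-point score in section 5.3 is an acceptable alternative.
2. Move concordance and kappa to descriptive secondary endpoints.
3. Declare that the change was made after results from the first 80 patients, which section 2.3 already summarises.

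**Cost.** No new scans or patients: 10.1 and 10.2 already require the three binary variables. The cost is wording, a primary analysis that is openly post hoc for the first 80, and limited precision. For 26 to 65 cases the expected half-width of the score interval for the sensitivity difference is about 16 down to 8 points (K = 0.11), or 22 down to 13 points (K = 0.30). For specificity it is about 7 to 9 points with 104 down to 65 controls, assuming 10% discordance and no true difference. The estimate and its interval must therefore carry the conclusion, not the test.
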